All patients undergoing surgery will be asked to participate in the study. No PHI would be needed for randomization. Patients will be approached in the office setting once they have decided to proceed with surgical management. The surgeon, fellow or clinical research team will approach the participants. Please see the roster for a list of participants involved in the consenting process. They will be handed a "study info" pamphlet that describes the purpose, methods and involvement of the study. The participants will then be scheduled for a preoperative visit. All patients who decide to have surgery are scheduled for a preoperative visit in our office, and patients will be reminded of the study and asked if they want to participate. If consent is granted, the patient will be randomized to receive the preoperative instructions verbally or via an instructional video." The surgeon, fellows and clinical research team are part of the research team.

18. Compensation: Will participants be compensated for their time? Describe the methods, amount and schedule for payment. What will happen to compensation if participants chose to withdraw? If no compensation is being offered, please justify why.

(Max ¼ page)

There is no patient compensation. The study involves no cost to subject participation.

19. Reimbursement: Will participants personally incur any expenses as a result of participation (e.g., fuel, missed work)? If no reimbursement is being offered, please justify why.

(Max ¼ page)

Patients will not incur any expenses as a result of participation.

20. Procedures

a) Describe how human participants will be involved in the research. If there is to be an intervention or interaction with the participants, describe what the researcher and participants will do, who will conduct the procedures, where and when the procedures will take place, how frequently, for how long, what equipment will be used, etc.

(Max ½ page)

Patients will be invited to participate in the study by principal investigator or co-investigator or designated study personnel (Appendix Project Roster) when the patient will be undergoing a minimally invasive gynecologic surgery.

Patient will be consenting in the clinic and randomization will take place the same day patient consent is obtained.

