The study group of patients will come to the clinic on the day of their surgery and be asked to watch the informational video about what to expect after their procedure and instructions on how to recover. They will be encouraged to ask their provider any follow up questions. [The instructional video is approximately 10 minutes long.](#)

The control group of patients will receive the standard patient education in place before the procedure and will also be able to ask to follow up questions from their provider.

Both groups will be scheduled for their routine two-week postoperative visit. Some patients schedule a telehealth postoperative visit, if a telehealth visit is scheduled, then a text or email will be sent. If the patient comes in person, the option of filling out the questionnaire in paper form, receive text or email to complete the survey. [The survey will take approximately 10 minutes to complete.](#)

Our primary outcomes will be patient level of satisfaction with the education they received prior to surgery and its impact on post-operative care which will be measured by the standardized likert scale (1 to 5 scale where 1 = strongly disagree and 5= strongly agree). The survey will include the following objective and subjective measures: Tylenol tablets used (over two weeks), Ibuprofen tablets used (over two weeks), pain scale (1 to 5 scale where 1 = none and 5= very severe). Additional information will be collected from the patient's medical records (ie. office visit notes, telephone encounters, hospital laboratory results, pain medication refill requests). Patients should continue any medication regimen as instructed by their physician up to the day of surgery. Patients will be treated for complications as they would have been treated otherwise. Study duration period will be approximately six months.

b) If you are using a dataset, please list out the variables you will be accessing. If you are using the Psychology Subject Pool, please list out the pre-screening data you will be collecting on your participants.

(Max ½ page)

[Chart review data: Age, Ethnicity, BMI, Smoking status, Narcotic use before surgery, Pain levels before surgery, Preop hemoglobin, Indication for surgery, Surgical procedure, Diagnosis, Presence of other pain disorders such as Interstitial cystitis, fibromyalgia, Intraoperative complications,](#)

[and Intraoperative blood loss.](#)

REDCAP Database will be used for the following purposes:

- Data collection

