- Sending links to view the video and questionnaire to patient(s)

21. Deception

a) Does this study involve deception or intentional lack of disclosure?

Yes X No

b) If YES, justify and indicate how participants will be debriefed. Indicate if participants are free to withdraw or selectively edit data after being fully debriefed. If NO, skip to the next question.

(Max ¼ page)

22. Research Results: If relevant, please describe what information/feedback, if any, will be provided to the subjects and/or communities after their participation in the project is complete. How will they be able to access the information? If relevant, describe the debriefing process.

Individual results will not be shared with subjects.

23. Consent Process - Ensure you are following the [UCR Informed Consent Guide](#). Sample Informed Consent Templates can be found on the [ORI Resources page](#).

a) Describe the process that will be used to obtain informed consent. How will it be recorded? Who will be authorized to conduct the process? Note that it's the quality of the consent that's most important not the format.

(Max ¼ page)

Consenting Process:

Patients will be approached when they are scheduling their surgery. Subject will be encouraged to take as much time as necessary to decide on participation on the study. They will be allowed to take an unsigned consent to review and discuss with family member. Subjects will be informed that no matter what they decide regarding participating, the care received from the physician will not be affected. Subjects will be randomized on the same day patient informed consent is obtained.

b) If you are applying for a waiver of documented consent (e.g., verbal, online, etc.) or a waiver or alteration of the consent process (e.g., not obtaining consent at all), please explain how you are meeting the conditions for the waiver or alteration as outlined in the [UCR informed Consent Guide](#).

(Max ¼ page) N/A

24. Will anyone other than the participants provide consent (e.g., parents, guardians, legally authorized representatives, etc.)? Describe the process by which capacity/competency will be assessed.

(Max ¼ page)

N/A

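### Randomisation is tied to a consent day that no section fixes, so a patient who signs early can be allocated, unblinded, before the arms are treated differently

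*Combined protocol and SAP*

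**What the plan says.** All references are to the combined protocol and SAP.

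- **Randomisation rule.** Section 20a: "Patient will be consenting in the clinic and randomization will take place the same day patient consent is obtained". Section 23a: "Subjects will be randomized on the same day patient informed consent is obtained".
- **First contact.** Section 23a: "Patients will be approached when they are scheduling their surgery". It adds: "Subject will be encouraged to take as much time as necessary to decide on participation on the study", and lets patients take an unsigned form away. Section 17: "Patients will be approached in the office setting once they have decided to proceed with surgical management", with a pamphlet handed over.
- **Second contact.** Section 17 says that at the preoperative visit "patients will be reminded of the study and asked if they want to participate", and then: "If consent is granted, the patient will be randomized to receive the preoperative instructions verbally or via an instructional video".
- **Delivery of the education.** Section 20a: "The study group of patients will come to the clinic on the day of their surgery and be asked to watch the informational video". Control patients receive standard education at some point before the procedure; the day is not given. Section 20b lists the sending of video links among the uses of REDCap.
- **What follows.** The survey is collected around the two-week postoperative visit (20a). The data of patients who withdraw are discarded (25). A total of 100 patients are to be enrolled (15), with no stated allowance for loss and no replacement rule, although section 29b expects some loss to follow-up.

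**The concern.** Randomisation works best when little can happen between allocation and the first difference in treatment. Here the trigger is the signature, and the signature can fall at more than one visit. Staff could follow the text exactly and randomise one patient on the day she books surgery and the next at her preoperative visit.

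Two things are at stake. First, a patient allocated early whose surgery is cancelled can never supply the primary outcome, which is satisfaction with the education and its effect on postoperative care. She has still been counted among the 100. Second, no blinding is described, the surgeon or fellow may be the person who takes consent, and the provider answers questions in both arms. While the arm is known but the education has not been given, patients may withdraw, or be given extra explanation, for reasons connected with the arm. Losses unrelated to the arm cost precision. Losses related to the arm can bias the comparison, and discarding the data of withdrawn patients removes the means of looking for it.

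**Working it through.** The point concerns sequence, so the main check is to set the sections side by side.

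**1. When is consent signed?** Section 23a places the approach, not the signature, at scheduling, and leaves the time to decide open. Section 17 describes an approach at about the same stage and a second request at the preoperative visit. Section 20a says only that consent is taken in the clinic. The signing day may therefore be scheduling, the preoperative visit or, as far as the text goes, some clinic day between them. Under the same-day rule, randomisation moves with it.

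**2. When do the arms first differ?** Section 20a puts the video in clinic on the day of surgery. Section 17 describes the allocation as the way the preoperative instructions are received, which could mean the preoperative visit. The REDCap links could deliver the video at another time. The control session has no stated day.

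**3. Combining the two:**

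- *Signed at scheduling.* The patient is allocated then and nothing differs until the preoperative visit at the earliest. There is a gap on any reading of step 2, unless the visits coincide.
- *Signed at the preoperative visit, both arms educated on the day of surgery.* There is a gap from that visit to surgery, unless they fall on the same day.
- *Signed at the preoperative visit, control education given there.* The allocation has to be known at that visit, so section 17 already gives the right time and a change of rule gains nothing for these patients.

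**4. Which events could later allocation keep out of the randomised set?** Those that occur before the first differing session: cancellation, a pregnancy found, a change of planned route, or a change of mind. Only cancellation necessarily leaves no postoperative survey. A patient switched to an open procedure is ineligible but can still answer it. Actual same-day discharge or overnight stay, conversion during surgery, and chemotherapy in the six weeks afterwards (all in section 15) are settled only during or after surgery. No time of randomisation before surgery resolves them.

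**5. Size.** The plan's 100 cannot be reproduced, because alpha, power, control value and SD are not given. Assuming two-sided alpha 0.05, 80% power and a 20-point absolute difference, the total runs from 98 (75% vs 95%) to 194 (40% vs 60%). The figure is neither confirmed nor refuted, and it does not decide the timing question.

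For scale only, assume a loss fraction L among 100 randomised 1:1, so n = 50(1 − L) per arm, with 70% vs 90% and two-sided alpha 0.05:

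power = Φ{[0.20 − 1.96·√(2·0.8·0.2/n)] / √[(0.7·0.3 + 0.9·0.1)/n]}

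- L = 0: n = 50, (0.20 − 0.1568)/0.0775 = 0.558, power 0.711
- L = 5%: n = 47.5, power 0.689; randomise 100/0.95 = 105.3, so 106, to keep 100 evaluable
- L = 10%: n = 45, power 0.665; randomise 100/0.90 = 111.1, so 112
- L = 20%: n = 40, power 0.612; randomise 100/0.80 = 125

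Every L here is an assumption. The documents give neither a cancellation rate nor the interval from either visit to surgery.

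**The case against.** The strongest reply is that sections 17 and 23a describe one sequence: approach and pamphlet when surgery is booked, time to think, then consent and randomisation at the preoperative visit. That reading is fair. A reader might infer that section 23a places consent at scheduling and so contradicts section 17. The text does not support this, since it places only the approach there and separates it from the signature. What remains is that nothing requires signing to wait for the preoperative visit, and the same-day rule then binds.

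A second reply is that later allocation may change nothing if control patients are taught at the preoperative visit. This also stands for patients who sign at that visit, but not for those who sign earlier. The plan does not say which reading of the education timing applies.

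A third is that allocation to a video of about 10 minutes or to verbal instruction is unlikely to affect cancellation, pregnancy or surgical route, and that the arm becomes known whenever it is released. Both are reasonable. Most such losses would cost precision rather than validity, and extra explanation by arm would remain possible after the change. Shortening the interval reduces the opportunity but does not remove it.

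**Conclusion.** The point holds as an ambiguity in the consent day combined with a rule that allows avoidably early allocation. It is a cheap improvement, not a fatal flaw. It rests on three things in the text: the same-day rule in sections 20a and 23a, the absence of a fixed signing visit, and the video on the day of surgery in section 20a.

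Three stronger conclusions should not be drawn. The sections are not shown to contradict each other. A loss of, say, 5 to 15 of the 100 cannot be read from the documents: any such range is assumed, depends on signing at scheduling, and would count ineligible patients who can still answer the survey as having no outcome. Nor does the consent day cause the whole eligibility problem, because several section 15 criteria depend on events during or after surgery.

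The size is therefore unknown and probably small. Under the assumptions shown, a 5% to 10% loss would take power from 0.711 to 0.689 or 0.665. The gain from the change depends on how many patients sign early and on when control education is given.

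**What to change.** - In sections 20a and 23a, replace the same-day rule. Consent may be taken at scheduling or later, but REDCap releases the allocation only after a re-check of the section 15 criteria that can be known before surgery: age, not pregnant, laparoscopic or robotic route planned, same-day discharge planned, surgery still scheduled. Release is immediately before the first education session that differs between arms.
- Reconcile sections 17, 20a and the REDCap video links, and state the day of control education, so that this session is defined for both arms.
- Record patients who consent but drop out before release as screen failures, and state that the 100 counts randomised patients.
- State separately how randomised patients are handled if they stay overnight, are converted to open surgery or receive postoperative chemotherapy. Later allocation does not settle these cases.

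The cost is wording in three sections and a short REDCap checklist. The downside is that the arm is not known at booking, so staff must be ready to deliver either form of education to any consented patient.

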Include any age, language, gender, or race-related inclusion/exclusion criteria and provide a justification for the use of these criteria. If applicable, please provide a rationale for your choice in sample size and/or sample size calculation.

If you are conducting research in languages other than English, translated versions of the participant-facing research materials (e.g., informed consent, recruitment materials, measures, etc.) must be submitted for review along with the [Certificate of Translation form](#).

(Max ¼ page)

Participants/Sample Size: Female patients who have been recommended for minimally invasive gynecologic surgery. A total of 100 patients will be enrolled in this study at UCR Women's Health Clinic. Statistical power. To rationalize the consideration of statistical power, we determined that 100 subjects will be needed to predict a difference of improvement in patient's post-operative experience ranges 20% or greater.

Inclusion criteria:

- Age 18 – 65 years old
- Surgery with UCR Gynecology physician
- Laparoscopic/robotic surgery
- Same day discharge after surgery
- Can read a survey in English
- Female

Exclusion Criteria:

- Receiving postoperative chemotherapy in the 6-week postoperative period
- Minors under the age of 18

- Postoperative overnight stay
- Laparotomy (open surgery)
- Pregnancy

16. Special Populations

a) Will any participants/subjects be specifically recruited from the following categories listed below (check all that apply):

Under the age of 18

Prisoners, probationers, or parolees

Pregnant women, fetuses, or neonates

Other characteristics that may cause them to be considered 'vulnerable' (e.g., cognitively impaired, educationally/economically disadvantaged, patients, students, staff, history of distrust, etc). Describe:

b) If YES, please justify the use of the above populations, and detailing what additional safeguards will be included in the study to protect the rights and welfare of the subjects and will there be direct benefits. If NO, skip to the next question.

(Max ¼ page)

17. Recruitment: Describe the mode of communication and how participants will be approached. Any recruitment materials, e-mails, & scripts must be submitted for review as appendices.

If you are recruiting participants through a subject pool (e.g., Psychology Department subject pool), please refer to the UCR [Policy on the Use of Subject Pools in Human Subjects Research](#).

(Max ¼ page)

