b) Describe the possible risks and consider the probability and magnitude of possible harms and discomforts. Describe the procedures that will be used to minimize potential risks to participants.

(Max ¼ page)

A remote unlikely risk is that the patient could feel more anxiety towards surgery despite the educational videos effort to calm patients concerns. The patient will be validated in her fears and reiterate that the video is meant to improve a patient's understanding regarding upcoming surgery. The patient will also be reassured that she can chose to be removed from the study at any point.

Ethical concerns may be associated with reviewing medical records of each participating patient but in order to prevent release of information improperly, each participating individual including physicians, nurses, receptionists, and the principal investigator will be certified under HIPPA and will properly exercise HIPPA regulations throughout the duration of this research.

- Only members of the study team will have access to the study data
- All study documents will be maintained in a secure location (i.e., a locked cabinet in the locked study coordinator's office [with limited access]) with only authorized research personnel affiliated with the study having access to it
- All electronic data will be stored on a password protected database with encryption, firewall, etc.

28. Possible Benefits

a) Describe possible direct benefits to participants. If there are no direct benefits, please state so. Please note that compensation is not a benefit.

(Max ¼ page)

Taking part in this study may or may not make benefit the subject's health. All reasonable efforts will be made to ensure the safety of each participant by following good medical practice guidelines. Any unanticipated risks will be addressed on a case-by-case basis.

b) Describe possible benefits to communities, society, or scientific knowledge in general.

(Max ¼ page)

The information from this study might help to develop better post operative experience after receiving concise information via video for future patients undergoing similar surgeries.

29. The US research regulations define '*Minimal Risk*' as the probability and magnitude of physical or psychological harm that is normally encountered in the daily lives, or in the routine medical, dental, or psychological examination of healthy persons. (45 CFR 46 & 21 CFR 50)

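### Section 20a prompts questions to the provider in the video arm only, while the primary outcome is a self-rated score from patients who know their arm

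*Combined protocol and SAP*

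**What the plan says.** All references are to the combined protocol and SAP.

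- **Outcome (section 20a).** "Our primary outcomes will be patient level of satisfaction with the education they received prior to surgery and its impact on post-operative care". It is scored on a "1 to 5 scale where 1 = strongly disagree and 5= strongly agree" and collected around the routine two-week visit.
- **Invitation to ask questions (section 20a).** For patients shown the video: "They will be encouraged to ask their provider any follow up questions". Control patients receive standard education and "will also be able to ask to follow up questions from their provider".
- **Response to anxiety (section 27b).** If a patient becomes more anxious despite the video, her fears are validated and staff "reiterate that the video is meant to improve a patient's understanding regarding upcoming surgery". The section describes this event as remote and unlikely. It gives no response for an anxious control patient.
- **Who is involved (section 17).** The surgeon, fellows and clinical research team approach patients and are also the research team. Patients are randomised to verbal instructions or a video.
- **Size (section 15).** "A total of 100 patients will be enrolled in this study at UCR Women's Health Clinic".

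The documents mention neither blinding nor a common script for staff.

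**The concern.** A patient cannot be unaware of whether she watched a video, and the primary outcome is her own opinion of the education she was given. Anything else that staff say or do differently by arm can therefore enter that rating directly. The invitation in section 20a covers every video patient and depends on no particular event. If staff actively urge questions in one arm and merely permit them in the other, the contrast becomes video plus prompted contact against standard education without the prompt. A satisfaction difference could then appear even if the video added nothing, and no analysis of the planned data could separate the two.

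The response in section 27b is a lesser matter of the same kind. It repeats the intended benefit of the material that the patient will later rate, and only in one arm.

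**Working it through.** **Step 1. The two arms side by side**

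| Element | Video arm | Control arm |
|---|---|---|
| Questions to provider (20a) | Encouraged, for every patient | Able to ask |
| Response to anxiety (27b) | Fears validated, purpose of the video restated | None written |
| Patient knows her arm | Yes | Yes |
| Primary outcome | Self-rated, 1 to 5 | Self-rated, 1 to 5 |

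The first row is a difference in a stated procedure that applies to the whole arm. The second can apply only to the few patients in whom the event occurs.

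**Step 2. Inputs for an illustration**

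The plan has no figure of its own on this point to reproduce.

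- Total of 100 patients: section 15.
- 50 per arm: assumes 1:1 allocation, since no ratio is stated, and no dropout.
- Two-sided 5% t-test on the mean score: assumed, since no test or significance level is stated.
- SD of 0.8 to 1.2: assumed, since none is given.
- Shift b in the video-arm mean from unequal prompting, 0.1 or 0.2 point: assumed. The documents give no basis for its true value.

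**Step 3. Unequal prompting across the whole arm**

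SE = SD × √(2/50) = 0.2 × SD, which is 0.16, 0.20 and 0.24 for SDs of 0.8, 1.0 and 1.2. With no true video effect, the test statistic is centred at b/SE instead of 0. The rejection probability comes from the noncentral t distribution with 98 degrees of freedom.

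| SD | b/SE at b = 0.1 | False-positive rate | b/SE at b = 0.2 | False-positive rate |
|---|---|---|---|---|
| 0.8 | 0.625 | 9.5% | 1.25 | 23.6% |
| 1.0 | 0.50 | 7.9% | 1.00 | 16.8% |
| 1.2 | 0.417 | 7.0% | 0.833 | 13.1% |

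The range is about 7% to 24%, against a nominal 5%.

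**Step 4. The section 27b response alone**

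If a share f of video patients receives it and each score moves by d, the arm mean moves by f × d. By the normal approximation, the rejection probability is Φ(fd/SE − 1.96) + Φ(−fd/SE − 1.96). Take f = 5% to 10%, d = 0.5 point and SD 1.0, all assumed:

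- f = 5%: shift 0.025, fd/SE = 0.125, rate 5.2%.
- f = 10%: shift 0.05, fd/SE = 0.25, rate 5.7%.

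For this response to move the whole-arm mean by 0.2 at f = 10%, each affected patient would have to change by 0.2/0.10 = 2 points on a 1 to 5 scale. The figures in step 3 therefore cannot be attributed to section 27b. They apply only to something that reaches the whole arm, such as the section 20a invitation.

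**The case against.** The best defence is that section 20a is a short answer on an IRB form and not a staff script. The word 'also' in the control sentence suggests that parity was intended, and controls who are instructed verbally already have live contact with staff. Nothing shows that video patients would have more provider contact overall. This has force: the difference may be loose drafting. But the two sentences differ as they stand, and staff could reasonably follow them as written.

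Three stronger readings are tempting and are not supported.

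- A reader might infer that the plan has staff promote the video to every patient in that arm. Section 27b is a conditional response to an event thought unlikely. It states a purpose without claiming superiority. A patient made more anxious by the video might also rate it lower, so even the direction is uncertain. Section 29b adds counselling on risks of watching the video, which is not promotional.
- A reader might infer that the pamphlet in section 17 tells controls that they received the lesser method. Its text is not in the documents, so its wording cannot be judged.
- A reader might take section 11 as evidence that provider contact drives satisfaction. As described there, the comparison was of interaction plus a video with an interview alone or with written material. Contact was present throughout, so it says nothing about the effect of prompting it.

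**Conclusion.** The point holds in a limited form. Section 20a writes an avoidable difference in prompting between arms, in a trial whose primary outcome is a self-rating by patients who know their arm. Section 27b adds a smaller difference that could barely move the arm mean by itself.

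The true size of the bias is unknown. The 7% to 24% range shows only how sensitive the comparison would be to a whole-arm shift of 0.1 to 0.2 point. It rests on the assumed shift, SD, test and allocation, and is not an estimate of what will happen. Nor do the documents show that staff wording in general favours the video, or that no part of the trial could be blinded: patients cannot be, but the plan is silent on survey handling and analysis. The case for acting is that the remedy is almost free and that the mixing cannot be undone once the data are collected.

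**What to change.** 1. In section 20a, use one identical sentence inviting questions in both arms.
2. In section 27b, write one response to an anxious patient for use in both arms, without restating what the video is meant to achieve.
3. Describe the study to patients neutrally, as a comparison of two ways of giving the same instructions. This matches how section 17 describes the randomisation and is consistent with the answer of no deception in section 21.

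The cost is small wording changes and a minor IRB amendment, with no added patients, visits or staff. The one downside is that patients hear less about what the investigators expect.
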